# **Exclusion criteria**

- History of organ transplant
- Wild-type TTR genotype
- Individuals who are non-ambulatory
- Prior treatment with any disease-modifying therapy (investigational or approved) alone or in combination, except tafamidis, as either VYNDAQEL 80 mg (four 20-mg tafamidis meglumine capsules) orally once daily or VYNDAMAX 61 mg (one 61-mg tafamidis capsule) orally once daily
- Peripheral neuropathy attributed to causes other than ATTR amyloidosis (eg, diabetes mellitus, B12 deficiency, HIV infection)

# 2.1.2. Data Source

The source of data for this study will be de-identified secondary data from an anonymized research database.

#### 2.1.3. Treatment/Cohort Labels

Not applicable.

## 2.2. Study Objectives

# Primary objective:

 To assess neurologic function before and after initiation of tafamidis, as either VYNDAQEL 80 mg (four 20-mg tafamidis meglumine capsules) orally once daily or VYNDAMAX 61 mg (one 61-mg tafamidis capsule) orally once daily, in patients with mixed-phenotype ATTRv-CM in a real-world setting.

## Secondary objective:

 To assess modified body mass index (mBMI) in patients with mixed-phenotype ATTRv-CM receiving tafamidis, as either VYNDAQEL 80 mg (four 20-mg tafamidis meglumine capsules) orally once daily or VYNDAMAX 61 mg (one 61-mg tafamidis capsule) orally once daily, in a real-world setting

# 3. HYPOTHESES AND DECISION RULES

## 3.1. Statistical Hypotheses

All analyses in this study are exploratory in nature and do not include formal hypothesis testing. This study will still report p-values at the 0.05 level.

#### 3.2. Statistical Decision Rules

The alpha level will be 0.05, 2-sided. No adjustments for multiple comparisons will be made.

#### 4. ANALYSIS SETS/POPULATIONS

#### 4.1. Full Analysis Set

The study will include all patients with mixed-phenotype ATTRv-CM who meet the study protocol I/E criteria and are treated with tafamidis, as either VYNDAQEL 80 mg (four 20-mg tafamidis meglumine capsules) orally once daily or VYNDAMAX 61 mg (one 61-mg tafamidis capsule) orally once daily for at least 6 months (with a ±3-month window). All patients meeting the below study enrollment criteria will be included in the full analysis dataset. It is estimated that at least 30 patients will be included in the analysis.

#### 4.2. Safety Analysis Set

Not applicable.

#### 4.3. Other Analysis Set

An analysis of available data may be conducted for scientific presentation at an international congress.

#### 4.4. Subgroups

Subgroup analysis may be considered by patient genotype if sample size allows.

#### 5. ENDPOINTS AND INDEPENDENT VARIABLES

# 5.1. Effectiveness Endpoint(s)

The primary study endpoint is neurologic disease progression, which includes neuropathy impairment score—composite score (NIS-CS), neuropathy impairment score—lower limbs (NIS-LL), polyneuropathy disability (PND) score, Medical Research Council (MRC) Scale for Muscle Strength score, and the Charcot-Marie-Tooth neuropathy score v2 (CMTNS2).

The secondary study endpoint is mBMI.

Table 1. Study Endpoints for Primary and Secondary Objectives

Variable	Role	Data source(s)	Operational Definition
Neurologic progression			
Neuropathy impairment score- composite score (NIS-CS)	Outcome	Research database	Data contains an assessment score for each muscle group or sensation area for motor strength/weakness, muscle stretch reflexes, and sensation. A final NIS-CS score will be calculated as a sum of these scores from the 3 sections ranging from 0 (normal) to 244 (total impairment), if data permits.
Neuropathy impairment score-lower limbs (NIS- LL)	Outcome	Research database	Same as above, NIS-LL will be calculated using individual assessment scores for motor strength/weakness, muscle stretch reflexes and sensation, from lower body only, ranging 0 (normal) to 88 (total impairment), if data permits.
Polyneuropathy disability (PND) score	Outcome	Research database	A scoring system of the patient's walking capacity. It consists of four stages from stage 0 (no impairment) to stage IV (confined to a wheelchair or bedridden).
Medical Research Council (MRC) Scale for Muscle Strength	Outcome	Research database	The MRC scale of muscle strength uses a score of 0 to 5 to grade the power of a particular muscle group in relation to the movement of a single joint.
Charcot-Marie-Tooth neuropathy score v2 (CMTNS2)	Outcome	Research database	Composite of nine assessments: symptoms (three items), signs (four items), and neurophysiology (two items). It is designed to measure length-dependent motor and sensory impairment in genetic neuropathies. Each assessment is scored on a $0-4$ point scale, reflecting severity of impairment. Patients are classified as mild (CMTNS $\leq$ 10), moderate (CMTNS $11-20$ ), or severe (CMTNS $\geq$ 20).
Overall health			
Height	Outcome	Research database	Height in centimeter or inches
Weight	Outcome	Research database	Weight in kilograms or pounds

Variable	Role	Data source(s)	Operational Definition
Body mass index	Outcome	Research database	Recorded or calculated in kg/m 
Modified BMI (mBMI)	Outcome	Research database	Calculated as the product of BMI in kg/m  and serum albumin in g/L to compensate for peripheral edema.

# 5.2. Safety Endpoints

Not applicable.

# 5.3. Other Endpoints

Not applicable.

# 5.4. Covariates

Patients' demographic and clinical characteristics will be collected in the pre-treatment baseline period.

Table 2. Study Covariates

Variable	Role	Data source(s)	Operational Definition
Patient demographics			
Age	Baseline characteristic	Research database	Patient age at baseline,* age groups will be determined by distribution of age.
Gender	Baseline characteristic	Research database	Male/Female
Race	Baseline characteristic	Research database	American Indian or Alaska Native/Asian/Black or African American/Native Hawaiian or Other Pacific Islander/White
Ethnicity	Baseline characteristic	Research database	Hispanic or Latino/Not Hispanic or Latino
Clinical characteristics			
Age at ATTR-CM diagnosis	Baseline characteristic	Research database	Age at diagnosis in years
TTR genotype	Baseline characteristic	Research database	Mutation in TTR gene associated with ATTR amyloidosis (eg, Val122Ile, Val30Met, Leu58His, Leu111Met)
Family history	Baseline characteristic	Research database	No family history/Parent/Siblings/Grandparent/ Other/Unknown
Comorbidities			
Charlson Comorbidity Index (CCI)**	Baseline characteristic	Research database	Based on comorbidities present at baseline*; grouped as 0, 1, 2, 3+

#### 6. HANDLING OF MISSING VALUES

For NIS-CS and NIS-LL neurologic progression endpoints, two assessments (one for left side, one for right side of body) should be reported for each muscle group or sensation area for motor strength/weakness, muscle stretch reflexes, and sensation subscales for each patient at the relevant timepoint. If the score on the left side of the body for a specific group/area is missing, and the score on the right is not missing, then the score on the right side could be used as score for the left side. The imputation could be applied vice versa. No further imputation will be performed when calculating final NIS-CS and NIS-LL total scores.

For mBMI, the pre-treatment value can be used to impute the missing post-treatment value for the same patient.

No missing data imputation will be performed for other neurologic progression or overall health endpoints.

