## 2.1. Study Design

This will be an observational, retrospective cohort study using structured secondary anonymized data. Patients with mixed-phenotype ATTRv-CM receiving tafamidis, as either VYNDAQEL 80 mg (four 20-mg tafamidis meglumine capsules) orally once daily or VYNDAMAX 61 mg (one 61-mg tafamidis capsule) orally once daily for at least 6 months, will be identified. Relevant data will be extracted through at least 6 months following the initiation of tafamidis treatment (with a ±3-month window).

The index date of this study is defined as the date of tafamidis treatment initiation with at least 6-month (and up to 12 months) pre-index period as the study pre-treatment baseline. Patients will be followed from index date for at least 6 months post-treatment (with a  $\pm 3$ -month window).

This study also includes three assessment windows in which the study endpoints will be extracted and evaluated. The pre-treatment assessment will be extracted at least 6 (and up to 12 months) prior to treatment initiation. The tafamidis initiation assessment will be obtained 3 months before or 3 months after the start of tafamidis treatment. The post-treatment endpoints will be assessed at least 6 months after (with a  $\pm 3$ -month window) treatment initiation.

The final study design will be determined based on feasibility assessment.

[figure not shown]

Figure 1. Overview of Study Design

\*Charcot-Marie-Tooth neuropathy score v2 (CMTNS2); mBMI: Modified body mass index; MRC: Medical Research Council; NIS-CS: Neuropathy impairment score-composite score; NIS-LL: Neuropathy impairment score-lower limbs; PND: Polyneuropathy disability.

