# 7.1.3. Analyses for Change from Baseline and Repeated Measured Endpoints

Continuous variables representing neurologic disease progression, such as NIS-CS, NIS-LL, PND, MRC, CMTNS2 and mBMI may be collected at multiple time points. Measures may be reported in the pre-treatment baseline period (at least 6 months (and up to 12 months) before treatment initiation), tafamidis initiation (within 3 months before or after treatment initiation), and post-treatment (at least 6 months after treatment initiation with a ±3-month window) as population mean, SD, median, first and third quartiles, and range in a table or chart format. If a participant had multiple values in one or more of the pre-defined periods, the mean value will be used in calculating the population-level summary statistics. More details of the number of assessments and assessment schedule will be finalized once the data structure is known.

PND and CMTNS2 scores will be summarized using a frequency table for both the pre-treatment and tafamidis treatment periods. Additionally, a shift table will be used to capture the change in PND and CMTNS2 scores between the two periods. The shift table will capture the changes at each visit relative to start of the period, ie, baseline for the pre-treatment period and tafamidis initiation visit for the tafamidis treatment period (within 3 months before or after treatment initiation).

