#### 7.2. Statistical Analyses

For the primary and secondary objectives, neurologic function, ie, NIS-CS, NIS-LL, MRC, CMTNS2, and mBMI will be examined in the full analysis set. If there is a sufficient number of patients with at least three neurologic assessments a linear mixed-effect model will be conducted to compare the rate of disease progression (within patient) between pre-treatment and tafamidis treatment periods. Patients must have at least three assessments to be included in the linear mixed-effect model (one in the pre-treatment period, one in the tafamidis treatment period, and one additional that can be in either pre-treatment or in the tafamidis treatment period). The linear mixed-effect model includes pre-treatment baseline score, treatment period, and their interactions with time as fixed effects, and the time-slope and intercept for each patient are included as random effects. Time is defined as number of months from pre-treatment baseline. The estimates of the monthly rate of change, along with the 95% confidence interval and the p value associated with the within group comparison comparing the pre-treatment and tafamidis treatment periods will be summarized.

However, if there is not a sufficient number of patients with at least three neurologic assessments, and many patients only have two assessments, then an approach is to take the first measurement and the measurement that fell within the window of the measurement in which majority of the patients had for the post-treatment assessment (whether they only have two or three or more) and test for significant statistical differences between the two assessments using an unpaired, or independent samples, t-test.

Alternatively, in the event there is an insufficient number of patients with three or more neurologic assessments, separate subgroup statistical analyses may be performed. This approach may use a between-subjects analysis of variance (ANOVA) for patients with at least three neurologic assessments and conduct unpaired, or independent samples, t-test for

patients with only two neurologic assessments. Descriptive summaries will be provided by treatment (pre-treatment or post-treatment), or by subgroups (if data permits) for each neurologic function endpoint.

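### Filling a missing post-treatment mBMI with the patient's own pre-treatment value sets that patient's change to zero and shrinks the group change by the share imputed

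*SAP*

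**What the plan says.** SAP section 5.1 is explicit about the role of the endpoint: "The secondary study endpoint is mBMI". Table 1 there defines it as BMI multiplied by "serum albumin in g/L to compensate for peripheral edema", so it needs a laboratory value as well as a weight.

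SAP section 6 then gives mBMI a rule of its own: "For mBMI, the pre-treatment value can be used to impute the missing post-treatment value for the same patient". The next sentence closes the door for everything else: "No missing data imputation will be performed for other neurologic progression or overall health endpoints". The only other imputation allowed is left/right substitution within the NIS scores.

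SAP section 7.2 names mBMI among the variables compared between the pre-treatment and tafamidis periods in the full analysis set. There are two main routes:

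- A linear mixed model of monthly rates: "If there is a sufficient number of patients with at least three neurologic assessments".
- Otherwise a two-point comparison, in which the analyst is to "take the first measurement and the measurement that fell within the window of the measurement in which majority of the patients had" after treatment, with an unpaired t-test.

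SAP sections 2.1 and 7.1.3 separate a pre-treatment window (6 to 12 months before initiation) from an initiation window (within 3 months either side). Of the third window, section 2.1 says: "The post-treatment endpoints will be assessed at least 6 months after" initiation, with a ±3-month allowance and no upper limit.

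**The concern.** The quantity of interest is the difference between before and after. Copying the before value into the after slot answers the question for that patient in advance: no change. In the two-point comparison the same number then stands on both sides.

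The rule can easily come into play. Inclusion in both documents depends on neurologic assessments, not on mBMI, so an eligible patient may have no post-treatment mBMI.

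The rule also sits badly with the rest of section 6. A missing BMI stays missing, while mBMI, which is calculated from it, may be filled. If only albumin is missing, the filled value ignores a post-treatment BMI that was observed.

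The SAP does not say which value is carried when a patient has both a 6-12-month value and an initiation value. It sets no condition for using the option, asks for no count of imputed values, and plans no sensitivity analysis.

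At stake is the reading of the secondary objective. Shrinkage towards zero is not safely conservative here: if mBMI is falling, false zeros look like stabilisation on treatment.

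**Working it through.** The plan has no mBMI effect, variance, missing share or sample-size calculation to reproduce. The inputs it does give are at least 30 patients (Protocol 9.5, SAP 4.1) and the assessment windows (SAP 2.1 and 7.1.3). Everything else below is an assumption and is marked as one.

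**1. Two-point comparison.** This is the likelier route, because Protocol section 5 says most patients are not expected to have several measures before or after treatment. Let m be the share imputed.

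Mean change with imputation = (1 - m) × observed mean change + m × 0 = (1 - m) × observed mean change.

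This is an identity and needs no assumed mBMI values. For 3, 6 and 9 of 30 patients the factor is 0.90, 0.80 and 0.70, whatever the direction of change.

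**2. Does imputing at least recover power?** Simulation, 20,000 runs. Assumed: n = 30, SD 150, pre/post correlation 0.9, true change -90, values missing at random, unpaired t-test as in SAP 7.2.

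| m | Mean change, imputed | Mean change, observed pairs | Mean t, imputed | Mean t, observed pairs | t smaller by |
|---|---|---|---|---|---|
| 10% | -80.9 | -89.9 | -2.12 | -2.26 | 6% |
| 20% | -72.0 | -90.0 | -1.87 | -2.14 | 12% |
| 30% | -63.1 | -90.1 | -1.63 | -2.01 | 19% |

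Percentages are from unrounded t values. With a true change of +90 the results mirror these. So the estimate is biased and no power is gained.

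**3. If missingness is related to mBMI.** Assume observed patients lost 50 units and the missing ones would have lost 100. At m = 20% the truth is 0.8 × (-50) + 0.2 × (-100) = -60, and the imputed analysis reports -40, or 67% of the true loss. At m = 30% it reports -35 against -65, or 54%. If the missing patients truly did not change, there is no bias.

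**4. Mixed model.** Assume a steady decline of d per month, no drug effect, and initiation mBMI observed at month 0 with value B. The value a months earlier is B + d·a. Carried to month b, it gives that patient an on-treatment slope of +d·a/b, which is a rebound. For the group:

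slope = (1 - m)(-d) + m(d·a/b) = -d[1 - m(1 + a/b)].

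The share of the decline falsely removed is m(1 + a/b). If the initiation value is carried instead, the imputed slope is 0 and the share is m.

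| a (months before) | b (months after) | 1 + a/b | Share removed at m = 20% |
|---|---|---|---|
| 12 | 3 | 5.0 | 100% |
| 12 | 6 | 3.0 | 60% |
| 9 | 9 | 2.0 | 40% |
| 6 | 12 | 1.5 | 30% |
| 6 | 24 | 1.25 | 25% |
| initiation value carried | any | 1.0 | 20% |

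b = 3 is the earliest visit the ±3-month allowance permits. As b grows, the share falls towards m.

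**5. Check of step 4.** Generalised least squares with random intercept and slope, a slope change at initiation, and the baseline score with its time interactions; 1,000 runs. Assumed: n = 30, d = 5 per month, SDs 150 (intercept), 3 (slope) and 40 (residual), all held at these values, and m = 20%. The true on-treatment slope is -5.

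| a/b | 6-12-month value carried | Formula | Initiation value carried (formula -4.0) | Observed data only |
|---|---|---|---|---|
| 12/3 | +0.07 | 0.0 | -4.17 | -4.94 |
| 9/9 | -2.96 | -3.0 | -3.99 | -4.95 |
| 6/24 | -3.77 | -3.75 | -4.00 | -5.01 |

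The SAP does not write the model out in full. The slope change at initiation is assumed, in line with the period start that section 7.1.3 uses for its shift tables: "tafamidis initiation visit for the tafamidis treatment period".

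**The case against.** **SAP 7.2 may already exclude these patients.** It expects some patients to fail the pre/post criteria, among other reasons for missing data points, and gives them descriptive statistics only. On that reading a patient without post-treatment mBMI is already left out. But the paragraph concerns patients who do not meet the inclusion criteria for the comparison, mainly for want of neurologic assessments. It does not override a rule written specifically for mBMI. The tension is real and is a reason to add a clarifying sentence.

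**The slope figures need several conditions at once.** The option must be used, the older value carried, the initiation value observed, mBMI falling, and the mixed model run. The 5m corner also needs a visit at month 3, which is the edge of the initiation window too. The protocol's inclusion footnote has no ±3-month allowance after treatment, and at b = 6 the maximum is 3m. This stands: the slope result shows what the rule can do and is not a forecast.

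**The factor (1 - m) is relative to patients with observed values.** It equals the bias only if missing patients would have changed like them. This stands. If missingness depends on health, an analysis of observed pairs can be biased as well.

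**The loss in t is specific to the unpaired test.** Also true. In a paired calculation at 30% imputed (assumed mean change -50, SD of change 100), t is 2.22 against 2.29, about 3% smaller. Imputation still gains nothing, although it makes precision look better (SE 15.7 against 21.8).

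**An endpoint-specific rule is not a contradiction.** Height, weight and BMI are not among the variables compared in SAP 7.2. That is fair, but the bias does not depend on the contrast with BMI.

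**The rule is optional, the endpoint secondary and the study exploratory.** This limits the severity. An option without a stated trigger, however, leaves the choice to be made with the data in hand.

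**Conclusion.** The concern holds. When the rule is followed, each imputed patient contributes a change of zero by construction, and the two-point mean change shrinks by exactly the share imputed relative to the observed patients: 10%, 20% or 30% for 3, 6 or 9 of 30. That is also the size of the bias if missingness is unrelated to mBMI; it is larger if the missing patients declined more.

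In the mixed model, under steady decline with no drug effect and an observed initiation value, the share of decline removed is m if the initiation value is carried and m(1 + a/b) if the older one is.

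The actual missing share and the course of mBMI are not in the documents, so neither the realised size nor the direction is known in advance. This should be fixed before the analysis. It does not touch the primary endpoint.

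**What to change.** - Delete the mBMI sentence from SAP section 6, so that mBMI is treated like the other overall health endpoints.
- Analyse observed mBMI in the mixed model, and patients with both values in the two-point comparison.
- Add one sentence to SAP section 7.2: an otherwise eligible patient who lacks only post-treatment mBMI is left out of the two-point mBMI comparison.
- Report the number of missing mBMI values in each period, with reasons.
- If carry-forward is kept at all, label it a sensitivity analysis, state which value is carried and report how many patients were imputed.

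The cost is one sentence removed, one added to section 7.2, and a table of missing counts. Fewer patients enter the two-point mBMI comparison (24 of 30 at m = 20%), a loss that imputation does not recover in the cases examined. Data collection is unchanged.

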#### 7. STATISTICAL METHODOLOGY AND STATISTICAL ANALYSES

#### 7.1. Statistical Methods

# 7.1.1. Analyses for Categorical/Binary Data

Categorical or binary variables including sex, race, ethnicity, age group at tafamidis initiation and at ATTR diagnosis, TTR genotype, family history, individual comorbid conditions, and CCI group will be summarized by using frequencies and percentages.

#### 7.1.2. Analyses for Continuous Data

Continuous variables including age at tafamidis initiation, age at ATTR-CM diagnosis, height, CCI score, and neuropathy scores will be reported using the summary statistics of mean, standard deviation (SD), median, first and third quartiles, and range. Change from baseline in neuropathy scores will be described using descriptive statistics. Continuous age and age at ATTR-CM diagnosis will be further categorized into age groups based on clinical knowledge and literature review. Variable distributions will be examined using summary measures, tables, and graphics, such as histograms and scatter plots, where appropriate. Variables will initially be used as they were obtained; however, transformation may be necessary or prove more informative. For example, continuous variables may be categorized, using common category boundaries found in the literature to stratify the data.

\*Baseline is defined as within 3 months prior to or 3 months following initiation of tafamidis. In the absence of baseline data within a  $\pm$  3-month window, data outside this window may be used to align with real world practice.

\*\*Individual comorbid conditions may be assessed based on feasibility assessment instead of CCI.

